4.3 Intervention

The intervention is the administration of a single dose of 150-200 MBq ^{68}Ga -RM2 (mass \leq 30 μg) for imaging purposes. This will be followed by a 30-40 min PET/CT study after a waiting period of 60 min (+/- 10 min). Prior clinical experience suggests that imaging can be performed within 1 hour post injection (27, 28). MR imaging and prostatectomy will be performed as standard of care at MSKCC.

If less than 150 MBq of ^{68}Ga -RM2 are synthesized due to technical difficulties, patient can be injected with that amount. However, only a limited PET/CT will be performed over the region of interest, over the pelvis with acquisition time per bed position adjusted to the lower amount of injected radioactivity.

5.0 THERAPEUTIC/DIAGNOSTIC AGENTS

The investigational product in this study is ^{68}Ga -RM2 (RM2), a [^{68}Ga] labeled peptide antagonist of the bombesin GRPr receptor, for positron emission tomography (PET) imaging of tumors. ^{68}Ga -RM2 will be synthesized, formulated and tested for release as described in section 7 of this IND application. The synthetic precursor for ^{68}Ga -RM2, RM2 (DOTA-4-amino-1-carboxymethylpiperidine-D-Phe-Gln-Trp-Ala-Val-Gly-His-Sta-Leu-NH₂) is provided by Piramal Life Sciences, Imaging Division (Berlin, Germany, <http://www.piramal.com>). Radiolabeling will be performed in the Radiochemistry & Molecular Imaging Probes (RMIP) Core Facility at MSKCC. A Letter of Authorization from Eckert & Ziegler Eurotope, granting FDA access to the Drug Master File (DMF) for the Ga-generator is provided in section 7 of this IND.

[figure not shown]

Figure 1. Chemical structure of ^{68}Ga -RM2

6.1 CRITERIA FOR SUBJECT ELIGIBILITY

6.2 Subject Inclusion Criteria

- Age ≥ 18 years
- Biopsy proven adenocarcinoma of the prostate
- Patients with low-risk, intermediate-risk and high-risk tumors according to NCCN guidelines (2.2014) will be included
- Planned radical prostatectomy at MSKCC
- Multiparametric MRI of the pelvis (performed or planned) as routine care

6.3 Subject Exclusion Criteria

Patients meeting any of the following exclusion criteria will not be eligible for study entry:

- Hematologic
 - Platelets $< 75\text{K}/\text{mL}$
 - ANC $< 1.0\text{ K}/\text{mL}$
- Hepatic laboratory values

- Bilirubin >2.0 x ULN (institutional upper limits of normal)
- AST/ALT >2.5 x ULN
- Renal laboratory values
 - Creatinine > 2.0 x ULN
- Claustrophobia interfering with MRI and PET/CT imaging
- Prior pelvic radiation
- Prior androgen deprivation therapy
- Patients deemed not surgical candidates due to prohibitive co-morbidities

7.0 RECRUITMENT PLAN

Potential study participants will be identified by a member of the patient's treatment team at MSKCC. Men of all races and ethnic groups will be considered for study participation. Candidates must conform to all inclusion and exclusion criteria to be accepted into the study.

If the investigator is a member of the treatment team, s/he will screen their patients' medical records for suitable research study participants and discuss the study and their potential for enrolling in the research study. Potential subjects contacted by their treating physician will be referred to the investigator/ research staff of the study.

During the initial conversation between the investigator/ research staff and the patient, the patient may be asked to provide certain health information that is necessary to the recruitment and enrollment process. The investigator/ research staff may also review portions of their medical records at MSKCC in order to further assess eligibility. They will use the information provided by the patient and/or medical record to confirm that the patient is eligible and to contact the patient regarding study enrollment. If the patient turns out to be ineligible for the research study, the research staff will destroy all information collected on the patient during the initial conversation and medical records review.

8.1 PRETREATMENT EVALUATION

- History and physical examination
- Vital signs
- Laboratory studies (within 2 weeks before study entry):
 - Complete blood count
 - PSA
 - Serum BUN, creatinine, AST, ALT, total bilirubin, alkaline phosphatase, and albumin
- Prostate MR imaging

9.1 TREATMENT/INTERVENTION PLAN

Drug Accountability

The investigator is obliged to keep sufficient documentation of the delivery and use of the investigational product. The documentation will include administration date/ time, calibration date/time, quantity, patient code, lot number and date of destruction. The investigator should maintain records that document adequately that the patients were provided the dose specified in the protocol and reconcile the medication received for the study. The label of each vial will contain the patient code and lot number, patient and radiopharmaceutical information will be entered in the radiopharmacy drug accountability forms. The investigator may assign some or all of the investigator's duties for drug accountability to an appropriate individual such as pharmacist or nuclear medicine technician who is under the supervision of the investigator.

9.2 PET/CT imaging

PET/CT imaging will be performed within two weeks prior to the planned prostatectomy.

No specific patient preparation is required before ^{68}Ga -RM2 injection. One intravenous catheter (Hep-Lock) will be placed by staff in the Molecular Imaging and Therapy Service for radiopharmaceutical administration.

^{68}Ga -RM2 preparation

Radiolabeling of ^{68}Ga -RM2. Labeling will be performed in accordance with the IND. The study will be performed under an FDA approved IND for ^{68}Ga -RM2; no studies will be performed until the IND is approved. The final product will contain 150-200 MBq ^{68}Ga and a total mass of less than 40 μg RM2. The investigational product label will include the patient name, MRN and the calibration date and time. The investigational product is to be used within 60 minutes after manufacturing.

Package Labeling and Formulation

Each vial will contain the following information on the label:

$[^{68}\text{Ga}]$ -RM2 Solution, IV

Lot #: $[^{68}\text{Ga}]$ -RM2- _____ IRB: _____

Activity: _____ mCi Volume: _____ mL

Production Date: _____ Production Time: _____

Expiration Date: _____ Expiration Time: _____

Store product at room temperature in a shielded container.
Caution: New Drug limited by federal law to investigational use.
Radioactive Material do not use if cloudy or contains particulate material.
MSK Radiochemistry and Molecular Imaging Probes Core

Images will be corrected for attenuation and scatter and adjusted for system sensitivity and providing parametric images in terms of standardized uptake values (SUV) (= MBq found/gm tissue / (MBq injected/gm body mass).

PET scanning: In order to provide reproducible clinical data, we will acquire all ^{68}Ga RM2 PET scans on a PET-CT scanner at MSKCC (same or a newer generation scanner). Intravenous injection of ^{68}Ga -RM2 (maximum of 200 MBq) will be given as a bolus. A PET-

CT scan extending from top of skull to mid thighs will be performed to determine the biodistribution 60 min (+/- 10 min) after injection. The low dose CT portion of the study will utilize 80 mA.

If less than 150 MBq of ^{68}Ga -RM2 is acquired and injected, only a limited PET/CT will be performed over the pelvis and acquisition times per bed position will be increased.

Because the diagnostic accuracy of RM2-PET/CT for detection of prostate cancer and prostate cancer metastases is currently not known, the result of the RM2-PET/CT will in general have no impact on patient management. However, in the special case of focal RM2 uptake in the bone marrow (outside the field of view of the prostate MRI), a dedicated MRI of the involved region will be discussed with the referring clinician and the patient. Because bone marrow is a frequent site for prostate cancer metastases and studies in normal volunteers have not shown any relevant RM2 uptake in the bone marrow, focal RM2 uptake in the bone marrow has to be considered as suspicious for metastatic prostate cancer. MRI is highly sensitive and specific for bone marrow metastases and is not associated with an additional risk for the patient. If bone marrow metastases are seen on MRI, patients are generally no longer treated with radical prostatectomy. Because radical prostatectomy is associated with significant morbidity, we would therefore consider it as ethically problematic not to further evaluate focal RM2 uptake in the bone marrow by MRI.

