3.4.4 Safety pharmacology studies

The pharmacological safety of ⁶⁸Ga-RM2 bombesin analog was subject to studies addressing effects on the central nervous system (integrated into extended single dose toxicity study), cardiovascular system and respiratory system. Since the studies were intended to address the effects of the chemical entity only, a mixture (500:1) of RM2 and stable Ga-RM2) which are the precursor and the non-radioactive analogue of ⁶⁸Ga-RM2 was dissolved in 0.9% NaCl and given to rats as a single intravenous injection. Doses were 0 (vehicle), 0.11, 1.05 and 10.5 mg/kg. The overall results of the in vivo safety pharmacology showed no adverse effects on central nervous system function and pulmonary function in rats. A transient slight increase in systolic and diastolic blood pressure was found immediately after administration of the high dose. The no observed effect level (NOEL) was 1.05 mg/kg suggesting a safety factor of 300 to the planned maximal human mass dose of 30 µg of the mixture of RM2 and ⁶⁸Ga-RM2 per patient (conversion based on body surface area).

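### Section 9.2 accepts a patient-labelled product with just under 40 µg RM2, although Section 4.3 caps the administered mass at 30 µg

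*Combined protocol and SAP*

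**What the plan says.** Section 4.3 defines the dose: "The intervention is the administration of a single dose of 150-200 MBq" of 68Ga-RM2, with the mass limited to 30 µg or less. Section 3.4.4 uses the same ceiling. It takes the rat no-observed-effect level of 1.05 mg/kg as "suggesting a safety factor of 300 to the planned maximal human mass dose of 30" µg, and it states that the 30 µg covers the mixture of RM2 and 68Ga-RM2 per patient.

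Section 9.2 describes the preparation. The final product holds 150-200 MBq "and a total mass of less than 40" µg RM2. It is labelled for one person: "The investigational product label will include the patient name, MRN and the calibration date and time". A second list in the same section begins "Each vial will contain the following information on the label" and has fields for lot, activity, volume, and production and expiry times. Neither list includes RM2 mass. The injection text sets a maximum of 200 MBq and gives no mass limit and no instruction to draw part of the vial.

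Two other sections bear on this. Section 9.1 asks the investigator for "records that document adequately that the patients were provided the dose specified in the protocol". Section 5.0 says that 68Ga-RM2 "will be synthesized, formulated and tested for release as described in section 7 of this IND application".

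**The concern.** The preparation section and the dose section give different mass figures, and nothing in the documents connects them. The people who prepare and inject the tracer work from Section 9.2. There they find a product limit above the dose cap, an injection limit stated in activity only, and labels that do not show the quantity needed to apply the cap.

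The consequence would be an avoidable dosing deviation from a product that meets Section 9.2 in full, together with an administered mass above the one on which the stated safety factor rests. Estimation of sensitivity and specificity is not at stake.

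**Working it through.** **1. The limits side by side**

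| Section | What is limited | Activity | RM2 mass |
|---|---|---|---|
| 4.3 | dose administered | 150-200 MBq | ≤ 30 µg |
| 3.4.4 | planned maximum human dose, mixture | not stated | 30 µg |
| 9.2, preparation | content of final product | 150-200 MBq | < 40 µg |
| 9.2, injection | dose injected | ≤ 200 MBq | not stated |

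A product of 30 µg or less satisfies every row. A product above 30 and below 40 µg satisfies both Section 9.2 rows and breaks the first two rows if all of it is injected.

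**2. Does the text imply injection of the whole product?** Three features say so. The product and dose activity ranges are identical, so no surplus is planned. The label names one patient. Section 4.3 provides that when synthesis yields under 150 MBq, the patient may receive what was made, which treats the synthesized and injected amounts as one. This remains an inference, because no sentence orders the whole vial to be given.

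**3. Excess over the cap if the whole product is injected** (mass / 30 − 1)
- 35 µg: 35/30 − 1 = 16.7%.
- 40 µg (limit, not reached): 40/30 − 1 = 33.3%.

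**4. Safety factor.** If 300 is taken as exact at 30 µg, it scales as 300 × 30 / mass:
- 35 µg: 300 × 30/35 = 257.
- 40 µg (limit): 300 × 30/40 = 225.

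The documents say that the conversion used body surface area but do not give its factors. Assuming a rat-to-human ratio of 6/37 and body weights of 60-70 kg:
- Human equivalent: 1.05 × 6/37 = 0.170 mg/kg, or 10,216 µg at 60 kg and 11,919 µg at 70 kg.
- Factor at 30 µg: 340 to 397, consistent with a stated 300 that was rounded down.
- Factor at 40 µg: 255 to 298.

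So 257 and 225 are the pessimistic end.

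**5. Human experience.** Section 11.1 reports a volunteer study that went up to 28 µg. The cap is 30/28 − 1 = 7% above that; 40 µg would be 40/28 − 1 = 43% above it.

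**6. What a partial draw would cost.** Assume a uniform vial of mass m and a draw holding 30 µg. The fraction drawn is 30/m.
- m near 40 µg: 30/40 = 75%. A 200 MBq vial yields 150 MBq; a 150 MBq vial yields 112.5 MBq.
- For the draw to hold 150 MBq, the vial needs 150 × m/30: 175 MBq at 35 µg and about 200 MBq near 40 µg.

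A draw below 150 MBq falls short of the activity required for the full scan.

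**The case against.** The strongest reply is that the two figures limit different things. Section 9.2 describes what the vial contains and Section 4.3 describes what the patient receives, so they do not contradict each other, and a dose cap need not be repeated in every section. That stands in part: the Section 4.3 cap governs administration throughout. It does not close the gap, because Section 9.2 gives no way to get from a 39 µg vial to a 30 µg dose.

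Section 9.1 helps further. Besides proof of the protocol dose, it requires quantity to be documented and product information to be entered in radiopharmacy accountability forms. A record therefore exists in which RM2 mass could be entered, though mass is not named as an item.

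The IND may also settle the matter. Release testing sits there, as may an aliquot rule or a tighter mass specification. It was not available for review, so how the vial is handled in practice cannot be judged. The mismatch printed in the protocol remains.

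One might try to reconcile the figures by reading 30 µg as 68Ga-RM2 alone and 40 µg as total RM2. Section 3.4.4 argues against this, since its 30 µg covers the mixture.

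A reader might instead infer that the protocol directs an overdose, or that patients face a material hazard. The documents support neither. Section 9.2 permits a product that could lead to a deviation; it does not order one. On hazard, the effect reported in the rat safety studies was mild: "A transient slight increase in systolic and diastolic blood pressure was found immediately after administration of the high dose", at 10.5 mg/kg, ten times the no-observed-effect level. Section 11.1 also describes a different GRPr antagonist given at roughly 560-13,440 µg/day with only local discomfort at the injection site.

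**Conclusion.** The point holds as an unreconciled dosing limit. Affected products are those above 30 and below 40 µg. The excess over the cap, if they are injected whole, is about 17% at 35 µg and approaches 33% near 40 µg. This rests on whole-product injection, which the text implies but does not state, and on the IND containing no rule that already prevents it.

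How often a product would exceed 30 µg cannot be determined from the documents. The direct safety effect is small: even the pessimistic scaling leaves a factor above 200. Confidence is high that the two sections do not match, and lower that the mismatch would produce deviations in practice. The change is optional but worth making because it is cheap.

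**What to change.** **Preferred.** After a check against the IND, change the product limit in Section 9.2 to at most 30 µg RM2, matching Sections 4.3 and 3.4.4. This is a one-sentence amendment. Do not resolve the mismatch by raising the administered cap to 40 µg: the stated safety factor rests on 30 µg, and the cited volunteer study stopped at 28 µg.

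**Only if the IND release limit must stay at 40 µg.** Keep 40 µg as a content limit, state in Section 9.2 that the injected mass must not exceed 30 µg, and put RM2 mass on the label or dose record so that the draw can be calculated.

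This route costs more than one sentence. A draw can fall below 150 MBq, and the limited pelvic scan that would follow still covers the prostate but gives up the skull-to-mid-thigh coverage. With it go the recording of uptake in bones and other organs outside the pelvis (Section 10.0, image data analysis) and the bone-marrow findings outside the pelvis that Section 9.2 considers ethically important to follow up. Section 4.3 allows the limited scan when synthesis falls short for technical reasons, so its wording would need extending to cover a deliberate partial draw.

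Neither route changes the sample size or the analysis.

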9.3 PET/MR coregistration

Mirada (www.mirada-medical.com) provides dedicated software to permit manual rigid and deformable registrations to align images acquired in separate sessions. We have used this software to register PET and MR datasets through anatomical co-registration of the low-dose CT scan of the PET/CT and MR data. The resultant transformation was then applied to the PET data. This co-registration capability will allow us to meet our primary objective of determining the distribution of radiolabeled bombesin in the prostate within a —sextantll model used previously by our group (29). In this model the prostate is divided in left/right base, left/right midgland and left/right apex. Each of these sextants is further divided into peripheral and transition zones. We acknowledge the imperfect nature of the —sextantll approach for localization, particularly on PET/CT where the normal anatomy is less well-delineated, but co-registration with MRI based on anatomical landmarks such as the urethra, verumontanum and ejaculatory ducts should minimize localization errors and improve imaging to pathology correlation.

9.4 Immunohistochemistry and gene expression analysis

The expression of GRPr by prostate tumors will be assessed with immunohistochemical staining as previously described (30, 31). Preliminary data in prostate tumor xenografts treated with androgen deprivation therapy suggest that GRPr expression is AR regulated (32, 33). Conversely, GRPr expression can induce androgen independent growth of prostate cancer cells (34). We will therefore stain the tumors for nuclear AR as well as for PSA (positively regulated by AR) and PSMA (negatively regulated by AR, (35)) in order to interrogate the relationship between GRPr expression, *in vivo* ^{68}Ga -RM2 binding, and AR signaling. Semiquantitative assays for AR and PSA are established at the prostate SPORE core lab. The relationship of GRPr and PSMA expression is also interesting from an imaging

perspective, because radiolabeled PSMA inhibitors have shown encouraging results in metastatic prostate cancer (36-38). Staining for PSMA and GRPr will allow us to evaluate whether PSMA and GRPr based PET imaging provide complementary information about tumor biology. This is suggested by previous studies which found that Gleason scores are negatively correlated with GRPr expression but positively with PSMA expression (18, 39). A recent study indicated that GRPr is a shared target gene of two ETS transcription factors that are involved in the development and progression of prostate cancer (ERG and ETV1) (40). ETS rearrangements are considered an early event in prostate carcinogenesis, which may explain the overexpression of GRPr in PIN and low-grade prostate cancers. Nuclear expression of ERG is a sensitive and specific marker for the presence of the TMPRSS2-ERG rearrangement and ERG mRNA expression (41). We will therefore stain the tumors for nuclear ERG using established protocols at MSKCC (41) and correlate the staining with GRPr immunohistochemistry as well as *in vivo* ⁶⁸Ga-RM2 binding. Loss of PTEN is closely linked to aberrant gene expression by ERG transcription factor rearrangements (42). Staining for PTEN will therefore also be included in our analysis.

FISH analysis: In order to further investigate the relationship between ETS and AR signaling, we will use FISH for the TMPRSS2-ERG fusion gene (43) to assess the type of rearrangement (i.e., whether it is by deletion or translocation). We will also use FISH to assess the tumors for ETV1 rearrangements and AR amplification using established protocols at the prostate SPORE core lab.

Gene expression analysis: We will determine GRPr mRNA levels of the tumors, normal prostate and benign prostate tumors and correlate those with GRPr immunohistochemistry and *in vivo* uptake of ⁶⁸Ga-RM2. We will also determine the RNA expression levels for AR regulated genes including PSA, HK2 TMPRSS2, FKBP5, STEAP and PSMA as a readout for AR output. This —AR signature will be correlated with uptake of ⁶⁸Ga-RM2.

10.0 EVALUATION DURING TREATMENT/INTERVENTION

Laboratory Safety Assessments

Hematology and blood chemistry assessments (CBC, PSA, serum BUN, creatinine, AST, ALT, total bilirubin, alkaline phosphatase, albumin, blood glucose levels, and serum testosterone level) will be done at the time points described in Table 2. Additional blood tests may also be performed at the discretion of the investigator for the purposes of investigation and follow-up of adverse events.

Physical examination

A physical examination including, but not limited to, general appearance, skin, neck, eyes, ears, throat, lungs, heart, abdomen, lymph nodes, extremities, and nervous system will be performed. The physical examination will include examination of known and suspected sites of disease. Physical examination results, height and weight will be recorded at baseline .

Vital Signs

Blood pressure and heart rate will be obtained at the time points outlined in the flowchart.

Table 2
 Schedule of Assessments

	Screening		Day 1 (day of PET/CT)	Day 2 (after PET/CT)
	Within 4 weeks before PET/CT	Within 14 days before PET/CT		
Informed consent	X			
Demographics	X			
Medical history	X			
Concomitant medications	X			
Physical exam	X			
Performance status	X			
Vital signs	X		X	
Routine MRI	X			
Laboratory studies ¹		X		
Follow-up over phone				X
⁶⁸ Ga-RM2 tracer administration			X	
⁶⁸ Ga-RM2 PET/CT scan			X	

¹ CBC, PSA, serum BUN, creatinine, AST, ALT, total bilirubin, alkaline phosphatase, albumin, blood glucose, serum testosterone

Image data analysis

PET and MRI exams will be evaluated by a nuclear medicine physician ([name]) and an experienced radiologist ([name]), respectively, blinded to the findings of the other imaging test, the biopsy results or any other clinical data except for the fact that the patient has prostate cancer.

PET/CT. The reader will record the level of suspicion for the presence of cancer in each sextant of the peripheral and transition zones using a 5-point index scale. The minimum intensity of uptake for a positive lesion (score > 1 on the 5 point scale) will be defined as mean uptake in normal prostate tissue plus two-times the standard deviation in prostate tissue without focal radiotracer uptake. Mean and maximum standardized uptake values will be recorded for each suspicious focus on PET. We will use ROC analysis to determine the sensitivity/specificity for prostate cancer detection by various visual scores and quantitative thresholds for lesion —positivity. Quantitative thresholds will be based on SUVs as well as lesion-to-background ratios. In addition to this analysis of the prostate, focal ⁶⁸Ga-RM2 uptake in lymph nodes, bones or other organs that is not explained by the normal biodistribution will be recorded.

MRI. Standard of care MRI studies at the Department of radiology are performed using a 3T whole-body unit. Transverse T1-weighted and transverse, coronal, and sagittal T2-weighted fast spin-echo sequences are obtained. Diffusion-weighted MRI is acquired in the transverse plane using a single shot spin-echo echo-planar imaging sequence with multiple b-values (b 0-1000). Dynamic contrast-enhanced MRI is performed using a transverse 3D T1-weighted spoiled gradient-echo sequence with a temporal resolution <7 seconds. Images are acquired after i.v. injection of 0.1 mmol/kg body weight gadolinium-DTPA at a rate of 2 mL/s. Based on these images the likelihood of prostate will be scored on a 5-point scale as described in several previous publication of the Department of Radiology, for example (29).

Joint analysis of PET and MR images. Following this independent reading of the MRI and PET images, a joint reading of PET and MR will be performed. This will allow us to localize the findings on PET to the prostate zonal anatomy on MRI. We will then also record the likelihood of cancer in each prostate region but now based on the combined information from the PET and MRI. This analysis is performed in order to evaluate if the combination of PET and MR imaging is more accurate than PET and MR alone. Since combined PET/MR scanners have recently been introduced it is clinically relevant to evaluate if the combination of ⁶⁸Ga-RM2-PET and MR is potentially more accurate for detection of prostate cancer than either ⁶⁸Ga-RM2-PET/CT or MR alone.

